1.0 Objectives

1.1 Objectives:

- Determine the rate of cesarean delivery in women who receive high-dose oxytocin regimen (HDOR) compared to women who receive low-dose oxytocin regimen (LDOR) for augmentation of labor.
- ii. Determine the rates of several measures of maternal morbidity in women who receive HDOR compared to women who receive LDOR. The measures of maternal morbidity that will be examined are labor duration (time interval from admission to labor and delivery to delivery of neonate), postpartum hemorrhage, and intrauterine infection.
- iii. Determine the rates of several measures of morbidity in neonates born to women who receive HDOR compared to women who receive LDOR. The measures will be examined as a composite outcome and will include perinatal death, umbilical cord arterial pH less than 7.0 or base excess greater than 12, Apgar scores at five minutes of less than <=3, admission to neonatal intensive care unit (NICU) for greater than 48 hours, severe respiratory distress requiring cardiorespiratory support and/or ventilation (intubation, continuous positive airway pressure, high-flow nasal cannula) for more than 12 hours, major birth injury (brachial plexus injury, bone fractures, other neurologic injury, facial nerve injury), neonatal encephalopathy, neonatal seizure, need for hypothermic treatment (cooling), and neonatal sepsis (positive blood, urine, or cerebrospinal fluid culture; or in the absence of positive culture(s), clinical evidence of cardiovascular collapse or an unequivocal X-ray confirming infection).
- 1.2 Hypothesis: The use of HDOR for labor augmentation will lower the incidence of dysfunctional labor and the subsequent need for cesarean delivery compared to the use of LDOR. We hypothesize that women who receive HDOR will have shorter labor durations, as well as lower rates of postpartum hemorrhage and intrauterine infection. Furthermore, we hypothesize that there will be no significant difference in morbidity in neonates born to women who receive HDOR compared to women who receive LDOR.

2.0 Background

One in three pregnant women undergo cesarean delivery in the United States.¹ Cesarean deliveries have increased at an alarming rate without a concomitant improvement in maternal and neonatal outcomes. Rather, the increasing rate has become a major health concern, as cesarean deliveries are associated with significant

Page 3 of 23 Revised Template: November 10, 2014

maternal morbidity, increased costs, and adverse implications for future pregnancies.²⁻⁴ The factor that has contributed the most to the increase in cesarean deliveries is the increased frequency of labor dystocia (i.e. dysfunctional labor due to ineffective uterine contractions).^{5,6} In an effort to avoid the need for a cesarean delivery when labor fails to progress, oxytocin is widely used to augment contractions. In fact, in 2003, 645,075 pregnant women (17% of all women in the United States who gave birth and were registered) received oxytocin augmentation. Though this statistic has no longer been reported in the CDC National Vital Statistics Reports since 2003, this percentage has likely further increased. While the total dose amount of oxytocin needed to produce a clinical response (i.e. progressive cervical dilation) may vary from patient to patient, the optimal dosing rate needed to achieve this endpoint has not yet been established.

Oxytocin dose protocols have been categorized into 'high' versus 'low' dose regimens, but these terms are to an extent, misnomers because the difference is typically in the rate of dose increase rather than the total dose used. Both protocols titrate the dose of oxytocin to achieve a frequency of uterine contractions (usually 4 to 5 contractions in a 10-minute interval) that is usually sufficient to result in progressive labor, and thus the target total dose should theoretically be similar. Numerous oxytocin dose protocols that vary in initial dose, incremental dose increase, and the time interval between dose increases have been studied. HDOR have been associated with significantly shorter labor duration and lower cesarean delivery rates, when compared to LDOR,⁷⁻¹³ without adverse effects on the newborn. It is postulated that by more rapidly progressing to the required therapeutic dose, cervical dilation is achieved more quickly, and the likelihood of a spontaneous vaginal delivery is increased. Furthermore, use of HDOR showed trends toward lower rates of postpartum hemorrhage and intrauterine infection for the mother.

Despite these positive findings, use of LDOR has become the prevailing obstetric practice in the United States.¹⁴ The preference for LDOR stems from unsubstantiated concerns that HDOR are associated with more uterine tachysystole (defined as more than 5 contractions in 10 minutes, averaged over a 30-minute window), which could lead to higher rates of neonatal morbidity.¹⁵⁻¹⁷ Prior studies have refuted this conclusion by showing similar neonatal outcomes when comparing use of HDOR and LDOR. However, the adoption of HDOR has been very uncommon due to persisting safety concerns and criticisms that prior studies had small sample sizes, inappropriate eligibility criteria, and inherent biases in study design.

As the frequency of cesarean deliveries performed for labor dystocia continues to increase, it is timely and critical to address the controversy surrounding the oxytocin dose regimens with an adequately powered prospective randomized trial. It is imperative that the study is double blinded to both care providers and patients to eliminate the subjective and unintentional biases that are likely contributing to the slow adoption of high-dose regimens that are effectively used for labor augmentation in other parts of the world.¹⁸

Page 4 of 23 Revised Template: November 10, 2014

The overarching goal of the proposed study is to conduct a double blind randomized trial to determine whether the use of HDOR is effective in lowering the incidence of cesarean delivery in a manner that is safe for both mother and neonate. Our data will allow us to help establish evidence-based guidelines for the optimal use of oxytocin for labor augmentation. Furthermore, this project will allow us to build a foundation for a program of research to study other approaches to the management of labor dystocia. Our long-term goal is to conduct research that will develop a better knowledge base to guide clinical decisions and encourage policy changes that can lead to safe prevention of cesarean delivery, both at Northwestern Memorial Hospital (NMH) and nationally.

3.0 Inclusion and Exclusion Criteria

3.1 Nulliparous women with singleton gestations who require oxytocin for labor augmentation will be recruited for the proposed study. Pregnant women who present to the Northwestern Memorial Hospital Prentice Women's Hospital (NMH-PWH) Obstetric Triage Unit for obstetric evaluation will be screened for eligibility. Subjects meeting eligibility criteria will be approached for potential recruitment, with the assent of their primary obstetric physicians and midwives, once their hospital admission for a trial of labor has been confirmed.

3.2 Criteria

- *i.* Inclusion criteria:
 - Able to give informed written consent
 - o Age ≥18 years
 - Nulliparous
 - Pregnant with a singleton gestation that is equal to or greater than 36 weeks.
 - Diagnosed with at least 6 regular uterine contractions within 60 minutes of observation. In addition, at least one of the following: cervix greater than or equal to 3 cm dilated or 80% effaced OR spontaneous rupture of membranes
 - Subject's attending obstetric physician or midwife has determined that the subject needs administration of oxytocin infusion for labor augmentation. Labor augmentation will be defined as stimulation of uterine contractions when spontaneous contractions have failed to result in progressive cervical dilation or descent of fetus.
- ii. Exclusion criteria:
 - History of prior cesarean section or uterine surgery
 - Fetus in non-cephalic presentation

Page 5 of 23 Revised Template: November 10, 2014

- Subject undergoing labor induction (i.e. receipt of cervical ripening with intracervical foley balloon placement or prostaglandins)
- Non-English speaking

3.3 Special Populations

- *i.* Adults unable to consent: Subjects who are unable to consent will not be included in our study.
- ii. Individuals who are not yet adults (infants, children, teenagers): Our study will only include subjects who are adults, and are 18 -45 years of age.
- *iii.* Pregnant women: This population will be included since our study is focused specifically on the obstetric population.
- iv. Prisoners: This is not applicable to our study; we will recruit solely from the population of pregnant women who deliver at Northwestern Memorial Hospital – Prentice Women's Hospital.
- **4.0 Study-Wide Number of Subjects** Not applicable
- **5.0 Study-Wide Recruitment Methods** Not applicable as this is a single-center clinical trial
- **6.0** Multi-Site Research Not applicable as this is a single-center clinical trial

7.0 Study Timelines

7.1 Timelines

- After informed consent is obtained, subjects will be enrolled in the study if and when their primary obstetric physician or midwife determines that oxytocin needs to be initiated for labor augmentation. The individual subject will be expected to participate in the study from the time of enrollment until time of discharge from the hospital after delivery.
- ii. Previous work by the principal investigator ([name]) showed that Active Management of Labor, with HDOR as one of its components, reduced the rate of labor dystocia and thus the rate of cesarean delivery, without increasing maternal or neonatal morbidity. This randomized trial was conducted at NMH and recruited 720 patients (75% of eligible women participated in the study) in a 12-month period. Recent hospital data revealed that 3,466 women in the 12-month period prior to the original study proposal would have meet eligibility criteria. As of July 22, 2019, 839women have been enrolled in this study.
- iii. The estimated date for completion of this study including primary analyses of the data is 4 years after the start of the clinical trial. Patient recruitment commenced in September 2015, and we expect to complete primary analyses by November 2019.

Page 6 of 23 Revised Template: November 10, 2014

8.0 Study Endpoints

- 8.1 Study Endpoints
 - i. Primary study endpoint:
 - The incidence of cesarean delivery
 - ii. Secondary study endpoints:
 - Measures of maternal morbidity
 - a. Length of labor duration (defined as the number of hours from admission to labor and delivery to delivery of neonate)
 - b. Incidence of postpartum hemorrhage (defined as an estimated blood loss greater than 500 mL for vaginal delivery or greater than 1000 mL for cesarean delivery)
 - c. Incidence of intrapartum chorioamnionitis (defined as fever great than 100.4° Fahrenheit in the intrapartum period with the initiation of a therapeutic antibiotic regimen in the intrapartum period)
 - d. Incidence of postpartum endometritis (defined as fever greater than 100.4° Fahrenheit in the postpartum period with the initiation of a therapeutic antibiotic regimen in the postpartum period)

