8.2 Safety Endpoints

- i. Primary safety endpoint:
 - Cesarean delivery performed for primary indication of nonreassuring fetal status
- ii. Secondary safety endpoints:
 - Measures of neonatal morbidity
 - a. Stillbirth or neonatal death
 - b. Umbilical cord arterial blood pH less than 7.0 or base deficit greater than 12 mmol/L; or cord venous blood pH less than 7.0 or base deficit greater than 12 mmol/L when umbilical artery values are not available.
 - c. Neonatal Apgar score at five minutes of life of less than 3
 - d. Admission to Neonatal Intensive Care Unit (NICU)

- i. Length of stay in NICU, if applicable
- e. Additional morbidities: severe respiratory distress requiring cardiorespiratory support and/or ventilation (intubation, continuous positive airway pressure, high-flow nasal cannula) for more than 12 hours, major birth injury (brachial plexus injury, bone fractures, other neurologic injury, facial nerve injury), neonatal encephalopathy, neonatal seizure, need for hypothermic treatment (cooling), and neonatal sepsis (positive blood, urine, or cerebrospinal fluid culture; or in the absence of positive culture(s), clinical evidence of cardiovascular collapse or an unequivocal X-ray confirming infection).

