9.0 Procedures Involved

- 9.1 Study Design: We propose a double blind randomized clinical trial:
 - i. Recruitment: Patients meeting eligibility criteria (as listed above) will be approached for potential recruitment, with the assent of their primary obstetric physician or midwife, once their hospital admission for a trial of labor has been confirmed.
 - Intervention: After informed consent is obtained, subjects will be ii. enrolled if and when their primary obstetric physician or midwife determines that oxytocin is to be initiated for labor augmentation. One group, labeled as LDOR, will undergo our primary institutional protocol (Protocol #12.0053) with a starting oxytocin concentration rate of 2mU/min that can be increased at increments of 2mU/min, as per the discretion of each individual's primary obstetric physician or midwife. The other group, labeled as HDOR, will undergo our supplemental institutional protocol for Active Management of Labor (Protocol #12.005m Appendix A) with a starting oxytocin concentration rate of 6mU/min that can be increased at increments of 6mU/min, as per the discretion of each individual's primary obstetric physician or midwife. The solutions used in the two groups will appear identical and volume infusion rates (2mL/hour) will be identical to ensure double blinding. The sole difference between the two groups will be the oxytocin concentration, with 30U oxytocin in 500mL of 0.9% normal saline (NS) in the LDOR group and 90U oxytocin in 500mL of 0.9% NS in the HDOR group. Once a patient is enrolled, randomized, and in receipt of the assigned intervention, further clinical management will be left to the discretion of each patient's primary obstetric physician or midwife. Each subject will have a unique drug code, which will remain with her for the trial duration, and

Page 8 of 23 Revised Template: November 10, 2014

- drug preparations will be labeled with the same unique code by the pharmacy.
- iii. Randomization: Fixed allocation procedure will assign the interventions to subjects with equal probability using a blocked randomization scheme without stratification. To maintain a double blind design, the NMH Investigational Pharmacy will carry out the randomization and preparation of oxytocin solutions according to the random assignment so that neither the patients and their care providers nor the investigators will know the identity of the intervention assignment.

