- 9.4 Clinical data that are pertinent to the study endpoints during the hospital stay will be collected (see 'data collection form'). There will be no long-term follow-up; the study period begins at randomization and ends with discharge from hospital following delivery. Data will be collected only up until time of each subject's hospital discharge.
- 9.5 Not applicable

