11.0 Data and Specimen Management

11.1 Data Analysis Plan: All outcome data will be collected and entered into the computer database before breaking the code and revealing intervention assignment. All analyses will be performed using the intention to treat principle. Descriptive statistics (means, standard deviations, proportions) will be calculated to check for any major differences in the study groups with regard to patient demographics and other baseline characteristics. All univariate comparisons will be unpaired and all tests of significance will be two tailed. For univariate analysis, continuous variables will be compared by Student's t-test. Categorical data will be compared using Chi-square testing or Fisher's Exact Test, depending on sample size. All values will be expressed as the mean + standard error (continuous variables) or as a percentage of the group from which they were derived (categorical variables). A p value of less than 0.05 will be considered statistically significant. An interim analysis of the first 100 patients will be performed by an independent expert physician, and the Havbittle-Peto rule will be used as a guide for stopping the trial if the analysis of the primary outcome demonstrates a significant difference between the group using a p <0.001. The overall type I error rate will be preserved at 0.05.

Page 11 of 23 Revised Template: November 10, 2014

- 11.2 Power Analysis: We based our power analysis on our previous work, literature review, and a review of recent institutional data. During the 12-month period prior to this proposal, the rate of cesarean delivery at NMH was 22.4% for nulliparous women with term singletons pregnancies who received oxytocin prior to delivery and had fetuses in the vertex presentation. For the purpose of the study design, a slightly lower rate was assumed for a population of women delivering at term that excluded women with history of prior uterine surgery and those undergoing induction of labor. A sample-size calculation suggests that, assuming a cesarean delivery rate of 20% in the traditional management LDOR group, 1002 patients (501 patients per group) would be required for this sample to provide 80% power to detect a decrease in the rate of cesarean delivery to 13.4% (one-third decrease) in the HDOR group. Chi-squared test comparing two independent proportions at a two-sided significance level of 0.05 is assumed in the power calculation.

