19.0 Setting

19.1

- i. Women who present to the NMH-PWH Obstetric Triage Unit for a chief complaint of "labor" or "spontaneous rupture of membranes" will be screened for study eligibility by a trained member of the investigative team when it has been determined by the primary care team that the patient will be admitted to the labor and delivery unit for labor management. Patients meeting eligibility criteria will be approached for potential recruitment, with the assent of their primary obstetric physician or midwife, once their hospital admission for a trial of labor has been confirmed. The study will be explained in detail and all questions will be answered prior to signing written informed consent to participate in the study.
- ii. Once informed consent is obtained, subjects will be enrolled into the study if and when their primary obstetric physicians or midwives have determined that oxytocin infusion is to be initiated for labor augmentation on the labor and delivery unit. It is at this point that subjects will be randomized into one of two intervention groups, as allocated by the NMH Investigational Pharmacy.
- iii. Not applicable
- iv. Not applicable

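### Labor duration is timed from admission and compared by an unadjusted mean: valid for total time, but it includes time before randomization and cannot separate faster labor from a change in cesareans

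*Combined protocol and SAP*

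**What the plan says.** Sections 1.1 and 8.1 define the endpoint in the same way. The objectives give it as "labor duration (time interval from admission to labor and delivery to delivery of neonate", and the endpoint list as "Length of labor duration (defined as the number of hours from admission to labor and delivery to delivery of neonate". Delivery by any route stops the clock. Section 1.2 hypothesizes a shorter duration with the high-dose regimen (HDOR).

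Randomization comes after admission. Under section 9.1 women are "enrolled if and when their primary obstetric physician or midwife determines that oxytocin is to be initiated for labor augmentation". Section 19.1 says of that moment, "It is at this point that subjects will be randomized into one of two intervention groups". Section 9.4 adds that "the study period begins at randomization and ends with discharge from hospital following delivery".

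For the analysis, section 11.1 says that "continuous variables will be compared by Student's t-test". The tests are unpaired, two-sided and by intention to treat, and results are given as mean and standard error. The plan describes no covariate adjustment, no interval from randomization to delivery and no time-to-event analysis. The primary safety endpoint in section 8.2 is "Cesarean delivery performed for primary indication of nonreassuring fetal status". That captures how many such cesareans occur, not when.

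**The concern.** The endpoint's clock starts before the treatment can act. Time between admission and randomization is balanced between arms in expectation, so it creates no false benefit, but its spread enters the standard error.

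The second issue is interpretation. The trial expects cesarean rates to differ by arm, and a cesarean ends the measured time. Section 14.1 foresees different kinds of cesarean in the two arms: for fetal heart rate indications with HDOR, and for labor dystocia with the low-dose regimen (LDOR). If cesareans come systematically earlier or later than vaginal births, a change in their number or timing moves the mean even when labor runs at the same speed. The net direction cannot be told from the documents.

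At stake are some precision on a hypothesized outcome and the ability to say why the means differ. A shift due to cesarean mix is a real difference in time to delivery, but it should not be reported as faster labor.

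**Working it through.** **The plan's own figure.** Section 11.2 gives 501 per arm for cesarean rates of 20% vs 13.4%, two-sided 0.05, 80% power. The pooled-variance formula without continuity correction returns 501 per arm (1002 in all), with power 0.801. It concerns cesarean delivery only. No SD, expected difference or power is given for labor duration, so every time input below is an assumption.

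**Validity.** A simulation with no treatment effect (3000 runs, assumed gamma-distributed times) rejected in 5.4% of trials timed from admission and 5.1% timed from randomization. The planned test holds its level.

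**Precision.** Let post and pre be the SDs of time after and before randomization, and ρ their correlation.

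- Total variance = post² + pre² + 2ρ·post·pre.
- SE of the difference = SD × √(2/501); the 95% half-width is 1.96 × SE.
- Power = Φ(Δ/SE − 1.96), with a negligible second tail.

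With post = 4 h and ρ = 0:

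| Clock | pre SD (h) | SD used (h) | Half-width (h) | Power, 0.75 h | Power, 1.0 h | Power, 1.5 h |
|---|---|---|---|---|---|---|
| Randomization | – | 4.00 | 0.50 | 84% | 98% | >99.9% |
| Admission | 2 | 4.47 | 0.55 | 76% | 94% | >99.9% |
| Admission | 3 | 5.00 | 0.62 | 66% | 89% | 99.7% |
| Admission | 4 | 5.66 | 0.70 | 56% | 80% | 98.7% |

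The two clocks break even at ρ = −pre/(2·post), which is −0.25, −0.375 and −0.50 for the three rows. Below those values the admission clock is the more precise.

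**Effect of adjustment.** Total time is pre plus post. Adding pre as a covariate therefore gives the same arm estimate whether the outcome is total or post-randomization time; only the coefficient of pre changes, by 1. The residual SD is post × √(1 − ρ²) on either clock. For 0.75 h:

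- ρ = 0: SD 4.00, power 84%.
- ρ = ±0.25: SD 3.87, power 87%.
- ρ = −0.5: SD 3.46, power 93%.

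A simulation (2000 runs per setting, pre SD 3 h) confirmed that the two adjusted estimates agree to rounding error. At ρ = −0.5 the standard error was 0.219 adjusted, 0.228 on the admission clock and 0.252 on the randomization clock.

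**Cesarean mix.** Hold the duration of each delivery type fixed and change only the rate. The mean shifts by (0.200 − 0.134) × gap, where gap is the difference in mean time between cesarean and vaginal labors. With total SD 5 h, SE = 5 × √(2/501) = 0.316 h:

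- Gap 2 h: 0.066 × 2 = 0.13 h, p<0.05 in 7% of trials.
- Gap 4 h: 0.066 × 4 = 0.26 h, 13%.
- Gap 6 h: 0.066 × 6 = 0.40 h, 24%.

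HDOR looks faster if cesareans come later than vaginal births, and slower if they come earlier. A simulated t-test with a gap of +4 or −4 h rejected in 13.2% of trials both ways.

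Two other patterns:

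- With 3 to 5 percentage points more cesareans under HDOR, each 4 to 6 h earlier, the mean moves by 0.03 × 4 = 0.12 h to 0.05 × 6 = 0.30 h (6.7% to 15.8%).
- With the HDOR rate at 13.4% and its cesareans moved by 1 to 2 h, it moves by 0.134 × 1 = 0.13 h to 0.134 × 2 = 0.27 h.

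**The case against.** The case for leaving the plan alone is substantial. The definition is consistent throughout, the comparison is unbiased, and no stated figure fails. Time from admission by any route is what the woman experiences, and it suits the inconvenience and cost considerations in sections 14.1 and 15.1. Section 2.0 postulates that cesareans fall because dilation is quicker, so a fall in cesareans with no change in labor speed is artificial. Section 14.1 lists foreseeable risks rather than forecasting rates. Cesarean numbers are already reported through the primary and primary safety endpoints. The larger power losses need inputs that the documents do not supply. Two extra analyses this late also bring multiplicity and a risk of choosing the better result.

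Most of this stands, and it limits the point to a secondary endpoint and to modest effects. It does not remove the point. The regimen cannot alter the pre-randomization interval, and adjusting for it is cheap. Cesarean counts do not reveal cesarean timing. The selection risk is met by fixing the lead result while still blinded. Section 11.1 leaves room for that: "All outcome data will be collected and entered into the computer database before breaking the code and revealing intervention assignment".

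**Conclusion.** The concern holds. The planned analysis validly compares mean total time on the unit. It may give up precision, and by itself it cannot attribute a difference to labor speed.

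The precision loss cannot be quantified from the documents. Under the assumed SDs with zero correlation it is material for effects of 0.75 h, slight for 1.5 h, and it reverses if the two intervals are negatively correlated enough. The cesarean-mix shift is modest: 0.066 h per hour of gap at the planned rates. The primary endpoint, its type I error and the sample size of 1002 are untouched. This is a worthwhile improvement rather than a flaw that threatens the trial.

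**What to change.** Keep admission-to-delivery time as the prespecified secondary endpoint. Before the code is broken, add:

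1. An analysis of the same endpoint adjusted for the admission-to-randomization interval as a baseline covariate, using infusion start only if randomization time was not recorded. In expectation it is at least as precise as either unadjusted version. State in advance whether the adjusted or the unadjusted result leads.
2. A supportive cumulative-incidence analysis of time from randomization to vaginal delivery, with cesarean as a competing event, read beside the mean. It shows when each type of delivery occurs in each arm, though it does not fully isolate labor speed.

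Derive the intervals before admission, delivery and enrollment dates are stripped from the database under section 11.3.

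**Cost.** This is a late addition. Section 7.1 reports 839 women enrolled by July 22, 2019 (839/1002 = 84%) and expects primary analyses by November 2019, so the change must be documented as made while blinded. Randomization or infusion-start times are needed for every woman. The data collection form is not among the documents, so their capture cannot be confirmed and some record extraction may be needed. No endpoint is replaced, and comparability with studies timed from admission is kept.
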